9.2. Dosage adjustments

Patients should be carefully monitored for toxicity. After the initial treatment cycle, dose reductions and/or administration delays will be decided using specific predefined rules to accommodate individual tolerance of treatment and maintain optimal dose intensity. All toxicities will be graded according to version 4.0 of the NCI CTCAE. Doses are to be adjusted based on the most severe toxicity that the patient experiences related or possibly related to the study treatment between each cycle of treatment. For hematological toxicities, the guiding principle is that the full doses of both drugs will be administered only if toxicities have recovered to ANC ≥ 1000/mm³ or and platelet count ≥ 100 000/L, or ANC ≥ 500/mm³ or and platelet count ≥ 75 000/mm³ in case of bone marrow disease, by day 21 after the start of the cycle

9.2.1. Vincristine, Irinotecan and Temozolomide

Dose levels for dose adjustment

Starting dose	Reduction (20%) dose level -1	Reduction (20%) dose level -2
Temozolomide		
125 mg/m ² /dx5 q 3 wks	100 mg/m ² /dx5 q 3 wks	75 mg/m ² /dx5 q 3 wks
150 mg/m ² /dx5 q 3 wks	120 mg/m ² /dx5 q 3 wks	90 mg/m ² /dx5 q 3 wks
Irinotecan		
50 mg/m ² /dx5 q 3 wks	40 mg/m ² /dx5 q 3 wks	30 mg/m ² /dx5 q 3 wks
Reduction (50%) dose level -1		
Vincristine		
1.5 mg/m ² /d (maximum 2mg) direct IV infusion at d1 and d8 q 3 wks (0.05 mg/kg for patient ≤ 10 kg)	0.75 mg/m ² (maximum 1mg) direct IV infusion at d1 and d8 q 3 wks (0.025 mg/kg for patient ≤ 10 kg)	

Study treatment dose reduction or discontinuation

Arm A (VI)

Type of toxicity	Dose modification at first occurrence	Dose modification at second occurrence

 ANC < 1000/mm³ or Platelet count < 100000/mm³ But recovered on day 21 after the start of a cycle 	
 No dose modification 	
 No dose modification

 ANC < 1000/mm³ or Platelet count < 100000/mm³ But recovered between 22 to 28 after the start of a cycle 	
 Decrease irinotecan to dose level -1 	
 Decrease irinotecan to dose level -2

 ANC < 1000/mm³ or Platelet count < 100000/mm³ But recovered between 29 to 34 after the start of a cycle 	
 Decrease irinotecan to dose level-2 	
 Discontinue study treatment

 Grade 3 and 4 diarrhea despite maximum loperamide therapy 	
 Decrease Irinotecan dose to dose level -1 If the same level of toxicity persists > 2 weeks despite suitable symptomatic treatment, discontinue study treatment If diarrhea is ongoing on day 21, delay next cycle for up to 2 weeks until diarrhea resolves to ≤ grade 1 If the diarrhea does not resolve after a 2-week delay, the patient should discontinue study treatment 	
 Decrease Irinotecan dose level -2 If the same level of toxicity persists > 2 weeks despite suitable symptomatic treatment, discontinue study treatment If diarrhea is ongoing on day 21, delay next cycle for up to 2 weeks until diarrhea resolves to ≤ grade 1 If the diarrhea does not resolve after a 2-week delay, the patient should discontinue study treatment

 grade 3 or 4 peripheral neurotoxicity (including paresthesia, severe movement disorder, paralysis, etc) and paralytic ileus 	
 If grade 3 or 4 peripheral neurotoxicity occurs (including paresthesia, severe movement disorder, paralysis, etc) and paralytic ileus, one injection of vincristine should be omitted and restarted at a 50% dose 	

 Other grade 3 non hematological toxicity * 	
 Decrease Irinotecan to level -1 	
 Discontinue study treatment

 Other grade 4 non hematological toxicity * 	
 Discontinue study treatment 	
 Not applicable

*For toxicities that are manageable or short-lived (i.e. grade 3-4 electrolyte abnormalities amenable to supplementation or grade 3 fatigue < 72 hours), the doses are not to be decreased.

Arm B (VIT)

Type of toxicity	Dose modification at first occurrence	Dose modification at second occurrence

 ANC < 1000/mm³ or Platelet count < 100000/mm³ But recovered on day 21 after the start of a cycle 	
 No dose modification 	
 No dose modification

 ANC < 1000/mm³ or Platelet count < 100000/mm³ But recovered between 22 to 28 after the start of a cycle 	
 Decrease temozolomide to dose level -1 	
 Decrease temozolomide to dose level -2 Decrease irinotecan to dose level -1

 ANC < 1000/mm³ or Platelet count < 100000/mm³ But recovered between 29 to 34 after the start of a cycle 	
 Decrease temozolomide to dose level -1 Decrease irinotecan to dose level-1 	
 Decrease temozolomide to dose level -2 Decrease irinotecan to dose level -2

 ANC < 1000/mm³ or Platelet count < 100000/mm³ On day 34 after the start of the cycle 	
 Discontinue study treatment 	
 Not applicable

 Grade 3 and 4 diarrhea despite maximum loperamide therapy 	
 Decrease Irinotecan dose to dose level -1 If the same level of toxicity persists > 2 weeks despite suitable symptomatic treatment, discontinue study treatment If diarrhea is ongoing on day 21, delay next cycle for up to 2 weeks until diarrhea resolves to ≤ grade 1 If the diarrhea does not resolve after a 2-week delay, the patient should discontinue study treatment 	
 Decrease Irinotecan dose level -2 If the same level of toxicity persists > 2 weeks despite suitable symptomatic treatment, discontinue study treatment If diarrhea is ongoing on day 21, delay next cycle for up to 2 weeks until diarrhea resolves to ≤ grade 1 If the diarrhea does not resolve after a 2-week delay, the patient should discontinue study treatment

 grade 3 or 4 peripheral neurotoxicity (including paresthesia, severe movement disorder, paralysis, etc) and paralytic ileus 	
 If grade 3 or 4 peripheral neurotoxicity occurs (including paresthesia, severe movement disorder, paralysis, etc) and paralytic ileus, one injection of vincristine should be omitted and restarted at a 50% dose 	

 Other grade 3 non hematological toxicity * 	
 Decrease both Irinotecan and Temozolomide to level -1 	
 Discontinue study treatment

 Other grade 4 non hematological toxicity * 	
 Discontinue study treatment 	
 Not applicable

*For toxicities that are manageable or short-lived (i.e. grade 3-4 electrolyte abnormalities amenable to supplementation or grade 3 fatigue < 72 hours), the doses are not to be decreased.

Considering that serious cases of liver injuries including some with fatal outcome have been reported with Temozolomide, in case of significant abnormalities of hepatic function, the benefits and risks to continue the treatment will have to be carefully examined by the investigator

9.3. Compliance

Vincristine and irinotecan will be administered intravenously. Information regarding the dates and doses of treatment administered will be recorded on the patient's medical record.

A pill count will be performed for temozolomide if dispensed for home use and documented on the pharmacy log.

9.4. Supportive concomitant therapy

9.4.1. Anti-emetics

The use of anti-emetic agents (e.g. ondansetron) for prophylaxis and treatment of nausea and vomiting is recommended. Further agents can be chosen in compliance with the conventional anti-emetic protocol at the center.

9.4.2. Anti-diarrhea medications

In the absence of any contraindications (ie known allergies), treatment with oral cefixime 8 mg/kg once a day (maximum daily dose 400 mg) is recommended and will be started 2 days before chemotherapy until day 7 (see Appendix 11 for cefixime management in The Netherlands).

Patients who have the onset of diarrhea during the irinotecan infusion or during the first 8 hours following the completion of infusion should receive a dose of atropine 0.02 mg/kg (maximum 0.25 mg) IV. Early onset diarrhea is usually preceded by diaphoresis, abdominal cramping and other cholinergic manifestations. Systematic prophylaxis is not recommended at the first cycle but is left to the investigator's judgment. Prophylactic treatment with atropine (0.02 mg/kg orally or IV, maximum 0.25mg) should be adopted before the next administration of irinotecan if the acute cholinergic symptoms including "early diarrhea" were severe during the prior cycle.

At the first sign of diarrhea starting > 8 hours after irinotecan administration, patients should begin intensive loperamide therapy. Each patient and/or patient's parent or legal guardian should be instructed to have anti-diarrheal medication readily available and begin treatment for diarrhea at the first episode of poorly formed or loose stools or earliest onset of bowel movements more frequent than normally expected for the patient. All patients and family members should receive written instructions for loperamide or racecadotril administration. Dosing is to be based on body weight. In addition, patients and family members should be instructed to contact their physician if any diarrhea occurs. Loperamide or racecadotril should be continued until a normal pattern of bowel movements returns.

Oral hydration with large volumes of water and electrolytes should be prescribed during the whole diarrhea episode. Loperamide prophylaxis and treatment of diarrhea must be implemented according to local clinical practice.

9.4.3. *Pneumocystis carinii* pneumonitis prophylaxis

Patients may receive co-trimoxazole according to centre guidelines.

9.4.4. Growth factor

Prophylactic use of granulocyte colony stimulating factor (G-CSF) is not recommended during the trial, however G-CSF may be used for patients presenting severe infection with neutropenia and in subsequent cycles after infectious complications.

9.4.5. Concurrent therapy

Concurrent administration of Irinotecan with an inhibitor (eg ketoconazole) or inducer (eg rifampicin, carbamazepine, phenobarbital or phenytoin) of the cytochrome P 450 3A4 metabolic pathway may alter the metabolism of Irinotecan and should be avoided.

Concurrent administration of St. John's wort is contraindicated.

Live attenuated vaccines are contraindicated during VI/VIT therapy and until six months after the end of the treatment

Administration of Yellow fever vaccine should be avoided during VI/VIT treatment (risk of severe peripheral neuropathy when concomitant administration with vincristine)

10. TRIAL PROCEDURE

10.1. Pre-treatment investigations

The pre-treatment investigations will determine patient eligibility and staging. The pre-treatment investigations must be performed no more than 1 week before the planned start of chemotherapy, except for radiological investigations which must be completed no more than 14 days before the planned start.

Type of Assessment	Delay

 Information, written consent form 	To be obtained before all specific procedure of the study

 Diagnosis, medical/oncology history and demographics : information on prior regimens, including dosing and duration of administration 
All clinical signs should be graded according to the NCI-CTC AEv4.0 (appendix 5)
	Before inclusion

CLINICAL EXAM
 
 Full physical examination Height, weight , body surface Vital signs : blood pressure after 5 min at rest, heart rate, temperature Performance status (Lansky Play Score or Karnofsky Score – appendix 3-4) 	To be completed < 7 days prior to the first study drug dose

LABORATORY TESTS*
 
 Complete blood count : white count (WBC), hemoglobin (HGB), hematocrit (HCT), differential count and platelet count Blood chemistry : glucose, urea, creatinine, total protein, albumin, Ca+, phosphorus and electrolytes (sodium, potassium, chloride and bicarbonate), AST, ALT, total bilirubin, alkaline phosphatase, LDH, GGT 	To be completed < 7 days prior to the first study drug dose

PREGNANCY TEST*
 
 Serum or urine pregnancy test 	To be completed < 7 days prior to the first study drug dose

RADIOLOGICAL AND OTHER INVESTIGATIONS**
 
 Computed Tomography (CT) scan or Magnetic Resonance Imaging (MRI) of the primary site. Volume estimation should be attempted by providing the maximum sagittal, coronal and axial diameters. MRI: Intravenous gadolinium administration is mandatory for all MRI examinations (post-contrast T1-weighted sequences should ideally be performed with saturation). MRI is particularly mandatory for limb, head/neck, pelvic and paraspinal masses. MRI appears to be superior to CT scan in defining soft tissue extension. CT scan: may be used for the assessment of thoracic or abdominal tumors. Bone scan or FDG-PET Scan recommended 	To be completed ≤ 14 days prior to the first study drug dose

- BM aspirates and trephine biopsies recommended mandatory in case of bone marrow disease

** All blood sampling will be made after application of topical anaesthetic cream, where appropriate*

*** It is mandatory to evaluate treatment response with the same imaging technique (CT or MRI) particularly where measurement is required. All imaging data should be loaded the CDs onto the PACS system for later review.*

10.2. Trial Period

10.2.1 Treatment procedures for first two cycles

The following procedures must be performed prior to dosing with Temozolomide in combination with Vincristine and Irinotecan on the days indicated during weeks 1-6. Blood sampling will be made after application of topical anaesthetic cream, where appropriate.

Type of assessment	Delay for first 2 cycles (during weeks 1-6)

CLINICAL EXAM
 
 • Full physical examination • height, weight , body surface • Vital signs : blood pressure after 5 min at rest, heart rate, temperature • Performance status (Lansky Play Score or Karnofsky Score – appendix 3-4) • Assessment of adverse events according to the NCI-CTC AE v.4.0 (appendix 5) • Recording of concomitant medications 	
day 1

LABORATORY TESTS*
 
 • Complete blood count : white count (WBC), hemoglobin (HGB), hematocrit (HCT), differential count and platelet count • Serum chemistries : glucose, urea, creatinine, total protein, albumin, Ca+, phosphorus and electrolytes (sodium, potassium, chloride and bicarbonate), AST, ALT, total bilirubin, alkaline phosphatase, LDH, GGT 	
days 1, 8, 15
 
If aplasia, blood counts should be performed as clinically indicated

RADIOLOGICAL AND OTHER INVESTIGATIONS
 
 • Tumor assessments (CT scan and/or MRI) including measurement of target lesion and assessment of response to treatment should be loaded the CDs onto the PACS system for later review. • Bone scan or FDG-PET Scan** • BM aspirates and trephine biopsies** 	
Mandatory after cycle 2

STUDY TREATMENT
 
 • Administration of vincristine to patient, given intravenously prior the administration of Irinotecan on day 1 and day 8. • Administration of irinotecan to patient given by 60-intravenous infusion on days 1 through 5. • According to randomization, temozolomide will be given orally, on empty stomach, one hour prior to administration of irinotecan on days 1 through 5 	

**Not necessary on day 1 of cycle 1 if screening blood draw performed within 7 days of the first treatment.*

***only repeated if clinically indicated or if initially involved or to confirm tumor response*

10.2.2 Treatment procedures for subsequent cycles

The following procedures must be performed prior to dosing with Temozolomide in combination with Vincristine and Irinotecan on the days indicated during weeks through all subsequent weeks that patient remains on study treatment (days 1, 8 and 15 based on 21 day cycles). Blood sampling will be made after application of topical anaesthetic cream, where appropriate.

Type of Assessment	Delay for subsequent cycles

CLINICAL EXAM
 
 • Full physical examination • height, weight , body surface • Vital signs : blood pressure after 5 min at rest, heart rate, temperature • Performance status (Lansky Play Score or Karnofsky Score – appendix 3-4) • Assessment of adverse events according to the NCI-CTC AE v.4.0 (appendix 5) • Recording of concomitant medications 	
day 1

LABORATORY TESTS
 
 • Complete blood count : white count (WBC), hemoglobin (HGB), hematocrit (HCT), differential count and platelet count 	
days 1, 8, 15.
 
If aplasia, blood counts should be performed as clinically indicated

 • Blood chemistry : glucose, creatinine, electrolytes (sodium, potassium, chloride and bicarbonate), AST, ALT, total and direct bilirubin, ASAT-ALAT, creatinine 	
day 1 if normal during cycles 1 and 2.
 
If significantly abnormal during cycle 1 or 2, blood chemistry should be taken on days 1, 8 and 15 for all subsequent cycles after cycle 2

RADIOLOGICAL AND OTHER INVESTIGATIONS
 
 • Tumor assessments (CT scan and/or MRI) including measurement of target lesion and assessment of response to treatment should be loaded the CDs onto the PACS system for later review. • Bone scan or FDG-PET Scan* • BM aspirates and trephine biopsies* 	
Mandatory after completion of every two cycles (must assess at 5 weeks after cycle 2 for responding or stable disease)


STUDY TREATMENT
 
 • Administration of vincristine to patient, given intravenously prior the administration of Irinotecan on day 1 and day 8. • Administration of irinotecan to patient given by 60-intravenous infusion on days 1 through 5 • According to randomization, temozolomide will be given orally, on empty stomach, one hour prior to administration of irinotecan on days 1 through 5 	

**only repeated if clinically indicated or if initially involved or to confirm tumor response*

10.2.3 End of study treatment / Withdrawal procedures

The duration of study participation is a maximum of 12 cycles. However, the continuation of treatment can be individually discussed with the investigator for patients who do not experience progression of disease after 12 cycles.

The following evaluation is performed 3 weeks after the last cycle of chemotherapy or at the end of study (see 7.2.).

Type of Assessment	Delay for End of Study treatment or Withdrawal

CLINICAL EXAM
 
 • Full physical examination • height, weight, body surface • Vital signs : blood pressure after 5 min at rest, heart rate, temperature • Performance status (Lansky Play Score or Karnofsky Score – appendix 3-4) • Assessment of adverse events according to the NCI-CTC AE v.4.0 (appendix 5) • Recording of concomitant medications 	
To be performed 3 weeks after the last cycle of chemotherapy or at the end of study

LABORATORY TESTS
 
 • Complete blood count : white count (WBC), hemoglobin (HGB), hematocrit (HCT), differential count and platelet count • Serum chemistries : glucose, urea, creatinine, total protein, albumin, Ca+, phosphorus and electrolytes (sodium, potassium, chloride and bicarbonate), AST, ALT, total bilirubin, alkaline phosphatase, LDH, GGT 	
To be performed 3 weeks after the last cycle of chemotherapy or at the end of study

RADIOLOGICAL AND OTHER INVESTIGATIONS
 
 • Tumor assessments (CT scan and/or MRI) including measurement of target lesion and assessment of response to treatment should be loaded the CDs onto the PACS system for later review. • Bone scan or FDG-PET Scan* • BM aspirates and trephine biopsies* 	
Mandatory
 
To be performed 3 weeks after the last cycle of chemotherapy or at the end of study, except documented previous disease progression

**only repeated if clinically indicated or if initially involved or to confirm tumor response*

10.2.4 Follow-up visit

Patients will be followed every 3 months for at least 2 years and then every 6 months during the subsequent 3 years or until death or lost to follow up until the date of the study cut-off, for the following:

- Patient status determination
- Tumour assessments including measurement of target lesion and assessment of response to treatment should be loaded the CDs onto the PACS system for later review.

11. OUTCOME MEASUREMENTS

11.1. Efficacy and treatment administration endpoints

11.1.1. Objective tumour response and progression

Measurements of all lesions should be recorded in metric units. All baseline evaluations should be performed as closely as possible to the treatment start, within 14 days of the beginning of the treatment if possible. The same radiological modality and technique (same sequence) for assessing disease at study entry is to be used for reassessment so that a direct comparison can be made to accurately evaluate disease response.

This study will use volumetric measurements of the primary tumour using an elliptical model (0.52 times the product of the 3 largest perpendicular diameters in the axial, coronal and sagittal plane) to assess response to neo adjuvant therapy. The RECIST 1.1 (Response Evaluation Criteria in Solid Tumours; *ref New response evaluation criteria in solid tumours: Revised RECIST guideline (version 1.1) European Journal of Cancer 45 (2009) 228–247*) criteria will be used for assessment of the size of measurable metastases, including nodal metastases (see Section 10.1.3.).

Primary Tumour Response (Volumetric)

On the basis of previous reports showing that volumetric tumour measurements may be more accurate than bidirectional or unidirectional measurements for tumours measuring $>35 \text{ cm}^3$, we will obtain volumetric measurements of the primary tumour using the formula for an ellipsoid model: volume 0.52 (antero-posterior diameter x transverse diameter x length) [Sohaib 2000, Prasad 2002].

Tumour volume (V) calculation:

a = length (in cm)

b = width (in cm)

c = thickness (in cm)

$$V = \pi/6 \times a \times b \times c = 0.52 \times a \times b \times c \text{ in cm}^3$$

It is planned to also measure the maximum uni-dimensional measurement as suggested by the RECIST 1.1 guidelines (*European Journal of Cancer 2009; 45: 228-47*) and later compare the volume with uni-dimensional measurements in terms of tumour response. The maximum lesion diameter in any plane should be recorded as the longest tumour diameter and measurements may be taken from CT or MRI, but the maximum tumour measurement must always be in the same plane (axial, coronal or sagittal) even if this results in measuring the lesion at a different slice level or in a different orientation or vector compared with the baseline study.

A clinical assessment should be done at each visit in order to detect tumour progression at any point during treatment. This should be supplemented by radiological examination as appropriate.

RELATIONSHIP BETWEEN CHANGE IN SINGLE DIAMETER (RECIST), PRODUCT OF TWO DIAMETERS (WHO), AND THREE PERPENDICULAR DIAMETERS ("VOLUME")

	Diameter, 2R	Product,(2R) ²	Volume, 4/3πR ³
Response	Decrease	Decrease	Decrease
	13%	24%	33%
	30%	50%	65%
	50%	75%	87%
Disease Progression	Increase	Increase	Increase
	12%	25%	40%
	20%	44%	73%
	25%	56%	95%
	30%	69%	120%

Response evaluation criteria (Volumetric)

Complete Response (CR)	Complete disappearance of all visible disease
Partial Response (PR>2/3)	≥ 65% reduction of tumour volume (volume response between 65-99%)
Minor Partial Response (PR<2/3)	Volume response between 34-64%
Stable Disease (SD)	No criteria for PR or PD
Progressive Disease (PD)	Any increase of more than 73% of any one target lesion/tumour volume or appearance of new lesions.

All responses must last at least 4 to 5 weeks without evidence of tumour progression or relapse.

Metastatic Disease Measurement

The RECIST 1.1 (*European Journal of Cancer 2009; 45: 228–47*) criteria will be used for assessment of the size of measurable metastases, including nodal metastases.

RECIST Methodology

Planes and techniques:

- CT: The same method of assessment and the same technique should be used to characterize each identified and reported lesion at baseline and during follow-up. Lesions should be measured on the same window setting on each examination.
- MRI: Lesions must be measured in the same anatomic plane by use of the same imaging sequences on subsequent examinations.

Measurements:

DIAGNOSIS

- **Measurable lesion:** A lesion that can be accurately measured in at least 1 dimension with the longest diameter at least twice the thickness of the CT or MR slice with a minimum of 10 mm (for lymph nodes ≥15 mm shortest axis). This is defined as a "**target lesion**". The investigator will identify up to 5 target lesions total and up to 2 per organ to be followed for response. In general, the largest lesions representative of involved organs are selected to follow as target lesions. However, in some cases, the largest lesions may not be easily measured and are not suitable for follow-up because of their configuration. In these cases, identification of the largest most reproducible lesions is advised. Serial measurements of

target lesions are to be done with CT or MRI. The sum of the longest diameters of all target lesions will be calculated and reported as the measurable metastatic disease measurement.

Non target: All other lesions (or sites of disease) including pathological lymph nodes should be identified as non-target lesions and should also be recorded at baseline and follow up.

- **Non-measurable:** All lesions that do not qualify as target lesions (all lesions whose largest diameter is less than twice the thickness of the CT or MRI slice, and all truly non-measurable disease such as bone lesions*, leptomeningeal disease, ascites, pleural/ pericardial effusions, lymphangitis cutis/pulmonis, and cystic lesions**).

Special note on lymph nodes:

Pathological nodes which are defined as measurable and may be identified as target lesions must meet the criterion of a short axis of ≥ 15 mm. Only the short axis of these nodes will contribute to the baseline sum. All other pathological nodes (those with short axis ≥ 10 mm but < 15 mm) should be considered non-target lesions. Nodes that have a short axis < 10 mm are considered non-pathological and should not be recorded or followed.

**Special note on bone lesions:*

Lytic bone lesions or mixed lytic-blastic lesions, with identifiable soft tissue components, that can be evaluated by cross sectional imaging techniques such as CT or MRI can be considered as measurable lesions if the soft tissue component meets the definition of measurability described above. All other bone lesions are considered non-measurable.

***Special note on cystic lesions:*

'Cystic lesions' thought to represent cystic metastases can be considered as measurable lesions, if they meet the definition of measurability described above. However, if non-cystic lesions are present in the same patient, these are preferred for selection as target lesions.

FOLLOW UP

- The same method of assessment is to be used to characterize each identified and reported lesion at baseline and during follow-up. Using the same plane of evaluation, the maximal diameter of each target lesion should always be measured at subsequent follow-up time points even if this results in measuring the lesion at a different slice level or in a different orientation or vector compared with the baseline study.

Metastatic Tumour Response

Target Lesions (RECIST):

- Complete Response (CR): Disappearance of all target lesions.
- Partial Response (PR): At least a 30% decrease in the sum of the longest diameters of all target lesions, taking as reference the disease measurement done to confirm measurable disease at study enrolment.
- Progressive Disease (PD): At least a 20% increase in the sum of the longest diameters of all target lesions, taking as reference the smallest disease measurement recorded since the start of treatment. In addition to the relative increase of at least 20% the sum must also demonstrate an absolute increase of at least 5mm (*Note: the appearance of one or more new lesions is also considered progression*)

- Stable Disease (SD): Neither sufficient shrinkage to qualify for PR nor sufficient increase to qualify for PD taking as reference the smallest disease measurement since the treatment started.

NOTES:

- *Lymph nodes* identified as target lesions should always have the actual short axis measurement recorded (measured in the same anatomical plane as the baseline examination) even if the nodes regress to below 10mm on study. This means that when lymph nodes are included as target lesions, the "sum" of lesions may not be zero even if complete response criteria are met, since a normal lymph node is defined as having a short axis of <10 mm.
- *When lesions 'fragment'*, the individual lesion diameters should be added together to calculate the target lesion sum. Similarly, as lesions coalesce, a plane between them may be maintained that would aid in obtaining maximal diameter measurements of each individual lesion. If the lesions have truly coalesced such that they are no longer separable, the vector of the longest diameter in this instance should be the maximal longest diameter for the 'merged lesion'.
- *Target lesions that become too small to measure*: All lesions (nodal and non-nodal) recorded at baseline should have their actual measurements recorded at each subsequent evaluation, even when very small (e.g. 2mm). However, sometimes lesions or lymph nodes which are recorded as target lesions at baseline become so faint on CT scan that the radiologist may not feel comfortable assigning an exact measure and may report them as being too small to measure. When this occurs it is important that a value be recorded in the case report form. If it is the opinion of the radiologist that the lesion has likely disappeared, the measurement should be recorded as 0mm. If the lesion is believed to be present and is faintly seen but too small to measure, a default value of 5 mm should be assigned. To reiterate, however, if the radiologist is able to provide an actual measure, that should be recorded, even if it is below 5mm.
- *If a lesion disappears and reappears* at a subsequent time point it should continue to be measured. However, the patient's response at the point in time when the lesion reappears will depend upon the status of his/her other lesions. I.e. the reappearance of an apparently 'disappeared' single lesion amongst many which remain is not in itself enough to qualify for PD: that requires the sum of all lesions to meet the PD criteria.

Non-Target Lesions:

- Complete Response (CR): Disappearance of all non-measurable (non-target) lesions
- Stable Disease (SD): The persistence of non-measurable disease without the development of new foci of tumour involvement.
- Progressive Disease (PD): Appearance of one or more new lesions and/or unequivocal progression of existing non-target lesions*

****Although a clear progression of "non target" lesions only is exceptional, in such circumstances, the opinion of the treating physician should prevail and the progression status should be confirmed later on by the review panel (or study chair).***

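### The volumetric progression row is worded to reach metastatic target lesions that RECIST scores on their sum, names no reference scan, and has no counterpart for the primary tumour in the overall-response table

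*Protocol*

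**What the plan says.** All references are to the protocol.

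- **Scope.** The opening of section 11.1.1 gives volumetry (ellipsoid model, three diameters) to the primary tumour and RECIST 1.1 to measurable metastases, including nodes.
- **Volumetric progression.** Under Response evaluation criteria (Volumetric), progression is "Any increase of more than 73% of any one target lesion/tumour volume or appearance of new lesions". No reference scan is named. Partial response in the same table is at least a "65% reduction of tumour volume (volume response between 65-99"%).
- **Target lesion.** The term is defined later in 11.1.1, under Metastatic Disease Measurement: a measurable lesion of at least 10 mm (nodes 15 mm in short axis), up to five in total. The summed longest diameters are the metastatic measurement.
- **RECIST response and progression.** Under Metastatic Tumour Response, partial response is "At least a 30% decrease in the sum of the longest diameters of all target lesions", against the enrolment measurement. Progression is "At least a 20% increase in the sum of the longest diameters of all target lesions", against the smallest measurement since treatment began, and "the sum must also demonstrate an absolute increase of at least 5mm". A note on a single lesion that reappears says of progression "that requires the sum of all lesions to meet the PD criteria".
- **Combination.** The table in 11.1.2 has separate columns for the primary tumour, target lesions, non-target lesions and new lesions. Its progression rows are triggered by the last three only.
- **Endpoint.** Section 11.1.3 defines the primary endpoint as complete or partial response after the first two cycles, confirmed within 4 to 5 weeks. It names the smallest measurement as the reference for progression, but only in the definition of best overall response.

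**The concern.** One defined term carries two progression rules. They differ in unit (one lesion or the sum), in absolute minimum (none or 5 mm) and in reference (unstated or the smallest value). A reader who takes the volumetric row at its word scores a metastatic lesion by its own volume. A reader who takes the RECIST paragraph at its word scores the sum. Both follow the protocol.

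The classification matters in several places. Progression instead of response after cycle 2 makes the patient a failure on the primary endpoint. Progression is also an event for PFS and time to treatment failure, ends the duration of response, and is a listed reason for withdrawal from study treatment (section 7.8). The revised decision rule in section 12.1 is a count, with 22 responders of 47 on VIT sufficient and 21 not. At that boundary one reclassified patient changes the side of the cut, although section 12.2 treats the cut points as guidelines.

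**Working it through.** **1. The protocol's own conversion.** If all three diameters scale together, volume change = (1 + diameter change)³ − 1.

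- Diameter +20%: 1.20³ − 1 = 72.8%, printed as 73%.
- Diameter −30%: 1 − 0.70³ = 65.7%, printed as 65%.

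So 73% is the volume equivalent of RECIST's 20%. Different thresholds for the two compartments are not in themselves a contradiction.

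**2. Literal reading: the volumetric row also covers metastatic target lesions.** Illustrative lesions of 50 and 12 mm become 25 and 15 mm.

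- Sum: 62 → 40 mm; 40/62 − 1 = −35.5%. This passes the 30% threshold, so partial response by the RECIST paragraph.
- Second lesion: (15/12)³ − 1 = +95.3% in volume. This exceeds 73%, so progression by the volumetric row.

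The same scan of the same lesions gets two opposite labels.

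**3. Which difference causes the clash?** Take 60 and 25 mm becoming 25 and 31 mm.

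- Sum: 85 → 56 mm; 56/85 − 1 = −34.1%, partial response.
- Second lesion: +6 mm, and (31/25)³ − 1 = +90.7% in volume, progression.

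This lesion has grown by more than 5 mm, so an absolute minimum would not remove the conflict. The cause is scoring one lesion against scoring the sum.

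**4. Scoped reading: volumetry for the primary only.** Against baseline, partial response needs a volume of at most 0.35 of baseline and progression needs more than 1.73. One primary tumour cannot meet both, so the clash in step 2 disappears.

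**5. What remains under the scoped reading.**

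- *Reference scan.* Let the primary's volume go 100 → 10 → 20. Against baseline the last scan is 20/100 − 1 = −80%, still a partial response. Against the smallest value it is 20/10 − 1 = +100%, progression. At the cycle-2 scan the planned earlier measurement is baseline, so the choice normally makes no difference there. It can matter at the confirmation scan and at every later one.
- *Missing table row.* Take primary progression, target lesions not progressing, non-target lesions not progressing, and no new lesions. No row of the 11.1.2 table matches. The rows that allow any result for the primary all require progression in another column or a new lesion.

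**The case against.** The strongest reply is that the protocol already separates the two rules. Section 11.1.1 states the scopes, the volumetric table sits within the primary-tumour material, the metastatic measurement is a sum of single diameters, and 11.1.2 uses separate columns. Section 10.1 asks for three diameters when imaging the primary site, whereas a RECIST target lesion needs only one, so the volume in the worked example might not be available. *Target lesion* is also used loosely elsewhere: section 7.4 speaks of a main measurable target lesion, and the visit schedules use the singular. Most of this stands, and the scoped reading is the likely intention. It does not settle the text. The row sets *any one target lesion* beside *tumour* as an alternative, and section 5.1 justifies the main evaluation criterion by the volumetric response of target lesions, which makes the literal reading a plausible one.

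A second reply is that the primary endpoint goes to one blinded central review (section 13.9), which limits disagreement between local and central readers on that endpoint. That also stands, but the panel still has to choose a rule, and sites act on progression during treatment.

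A reader might infer more: that the missing 5 mm minimum is the defect, and that measurement error on small lesions turns responders into failures. The documents do not support this.

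- Step 3 shows that the minimum does not cause the clash. Under uniform growth a 5 mm minimum alters the result only below 25 mm, where 20% is less than 5 mm.
- False progression calls above 73% arise for small *unchanged* lesions, which are non-responders either way. For a true responder at 0.35 of baseline volume, with an assumed error SD of 1.0 or 1.5 mm per diameter, a simulated false progression at cycle 2 occurs in no more than about 0.02% of cases at 10 mm and essentially never at 15 or 20 mm.
- Section 11.1.1 does say that "volumetric tumour measurements may be more accurate than bidirectional or unidirectional measurements for tumours measuring" more than 35 cm³, but section 5.1 gives a separate reason for using volume, namely surgical clearance. The size remark is not the sole basis.

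**Conclusion.** The point holds as a fault of scope and completeness in the progression criteria. Three items need reconciling: the volumetric row names lesions that another rule governs, it states no reference measurement, and the combining table omits progression of the primary tumour. The opposite labels in step 2 depend on the literal reading and on all three diameters scaling together. The lesion sizes are illustrative. The reference-scan and missing-row gaps remain on either reading.

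The protocol gives no lesion-size distribution, so the number of affected patients cannot be derived, and no effect on the response rate or on the operating characteristics of the design is shown. The point deserves correction because the labels feed the primary endpoint, PFS and response duration and the correction is almost free. It does not undermine the design.

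**What to change.** Before the final central read, reconcile sections 11.1.1, 11.1.2 and 11.1.3 so that one progression rule applies to each compartment:

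1. Following the scope already stated in 11.1.1, limit the volumetric progression row to the primary tumour by removing the reference to any one target lesion.
2. State the row's reference as the smallest volume recorded on study, consistent with the RECIST paragraph and with 11.1.3.
3. State that metastatic target lesions are scored by the RECIST sum rule.
4. Add a row to the 11.1.2 table for progression of the primary tumour.

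No absolute minimum for the volumetric row is proposed. Progression is a reason for withdrawal in section 7.8, so the sponsor should check that the reconciled wording and that section agree.

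The cost is a few lines of wording in the protocol and in the instructions to the review panel. The required diameters are already recorded, so no new measurement is needed.
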